#### **4.1.5 Blinding and procedures for unblinding**

##### **4.1.5.1 Blinding**

The trial will be conducted in an open-label. Blinding is not applicable. However, to reduce bias, the BI study team will be blinded from the aggregated Phase II data at the treatment level until the primary analysis for Phase II.

##### **4.1.5.2 Procedures for emergency unblinding**

Not applicable.

#### **4.1.6 Packaging, labelling, and re-supply**

BI 836858 will be supplied in 10 mL vials containing 100 mg BI 836858. For details of packaging and the description of the label, refer to the ISF. Medication will be delivered to

Proprietary confidential information.

© 2019 Boehringer Ingelheim International GmbH or one or more of its affiliated companies. All rights reserved.

This document may not - in full or in part - be passed on, reproduced, published or otherwise used without prior written permission.

the Investigator's pharmacy where the total dose per patient will be prepared upon request from the Investigator.

For preparation of BI 836858 infusion solution, the content of the vial of BI 836858 will be diluted in 0.9% sodium chloride. The content of several vials may be needed for administration of the requested dose. For further details, please refer to the instructions included in the ISF. The full volume of the diluted compound will be 250 ml.

#### 4.1.7 Storage conditions

BI 836858 has to be stored in a limited access area at the temperature indicated on the trial drug label. Do not freeze. If the storage conditions are found to be outside the specified range, immediately contact the local clinical monitor (CML) as provided in the list of contacts and reported in the ISF. For more details on BI 836858, please refer to the Investigator's Brochure (IB) and the ISF.

#### 4.1.8 Drug accountability

Drug supplies, which will be provided by the Sponsor or a Clinical Research Organization (CRO) appointed by the Sponsor, must be kept in a secure, limited access storage area under the storage conditions defined by the Sponsor. A temperature log must be maintained to make certain that the drug supplies are stored at the correct temperature.

Each Investigator and/or pharmacist will receive the investigational drugs delivered by the Sponsor when the following requirements are fulfilled:

- approval of the study protocol by the Institutional Review Board (IRB) / Independent Ethics Committee (IEC),
- availability of a signed and dated clinical trial contract between the sponsor and the Head of Trial Center,
- approval/notification of the regulatory authority, e.g. competent authority,
- availability of the curriculum vitae of the principal Investigator,
- availability of a signed and dated CTP or immediately imminent signing of the CTP,
- availability of the proof of a medical licence for the principal investigator,
- availability of the FDA Form 1572 if applicable.

These records will include dates, quantities, batch/serial numbers, expiry ('use by') dates, and the unique code numbers assigned to the investigational product(s) and trial patients. The Investigator and/or pharmacist must maintain records of the product's delivery to the trial site, the inventory at the site, the use for each patient, and the return to the Sponsor or alternative disposition of unused product. The Investigator/pharmacist will maintain records that document adequately that the patients were provided these doses specified by the CTP and reconcile all investigational product received from the Sponsor. At the time of return to the sponsor, the investigator must verify that all unused or partially used drug supplies have been either destroyed or returned by the investigational site, and that no remaining supplies are in the investigator's possession.

## 4.2 CONCOMITANT THERAPY, RESTRICTIONS, AND RESCUE TREATMENT

### 4.2.1 Rescue medication, emergency procedures, and additional treatment(s)

Rescue medication to reverse the action of BI 836858 is not available. Potential side effects of BI 836858 have to be treated symptomatically. Patients should receive supportive care according to the local guidelines regarding treatment of infusion-related reactions, blood product support, antibiotics, antivirals, analgesics, skin and mouth care, etc. The use of growth factors such as granulocyte colony stimulating factor (G-CSF) will be allowed (other than ESAs), but growth factors should be avoided during the first four administrations (2 cycles) for better assessment of safety and response parameters. G-CSF should not be given prophylactically.

Anti- bacterial and fungal prophylaxis should be given according to local standards or available guidelines.

All concomitant therapies to provide adequate care may be given as clinically necessary. All concomitant treatments will be recorded in the eCRF except for vitamins and nutrient supplements. Trade name, indication and dates of administration of concomitant therapies will be documented. For parenteral nutrition during the trial, the components need not be specified in detail. It should be indicated as 'parenteral nutrition'. If a patient needs anesthesia, it will be sufficient to indicate 'anesthesia' without specifying the details.

Concomitant therapy will be recorded in the eCRF during the screening and treatment period, starting at the date of signature of informed consent, and ending at the EOT-visit. After the EOT-visit, only concomitant therapy indicated for treatment of an adverse event needs to be reported.

After implementation of CTP version 5.0 collection of Concomitant Therapy information only if the indication is treatment of an (S)AE.

### 4.2.2 Restrictions

#### 4.2.2.1 Restrictions regarding concomitant treatment

Patients must not be receiving any concurrent treatment for MDS while on study. Exceptions will be made for supportive therapies such as transfusions or use of growth factors. The use of colony stimulating factor (G-CSF) will be allowed (other than ESAs), but growth factors should be avoided during the first four administrations (2 cycles) of BI 836858 for better assessment of safety and response parameters. G-CSF should not be given prophylactically.

Iron chelation therapy are permitted to those Phase II patients randomized to BSC only, however these treatments are not allowed for patients receiving BI 836858 in this study.

Short term glucocorticoid medications may be used as clinically indicated to treat infusion-related reactions at any dose. All other indications for steroids have to be discussed and agreed upon between Investigator and Sponsor.

#### 4.2.2.2 Restrictions on diet and life style

No restrictions apply with regard to diet, water intake or life style.

### 4.3 TREATMENT COMPLIANCE

BI 836858 will be administered as a single intravenous infusion under supervision of the Investigator or dedicated clinic personnel. Compliance may also be verified by pharmacokinetic assessment. Any discrepancies will be explained in the eCRF by the Investigator or designee.

## 5. VARIABLES AND THEIR ASSESSMENT

### 5.1 EFFICACY – PHARMACODYNAMICS

#### 5.1.1 Endpoints of efficacy

The efficacy endpoints will be assessed at the time points specified in the [Flow Chart](#).

For definition of response criteria please refer to [Section 5.1.2.3](#).

Primary Endpoint: (Phase II)

- RBC Transfusion Independency

Secondary endpoints: (Phase I)

- RBC Transfusion Independency

Secondary endpoints: (Phase I and II)

- Hematologic improvement neutrophils (HI-N)
- Hematologic improvement platelets (HI-P)
- Hematologic improvement erythroid (HI-E)
- Time to HI-E response
- Mean hemoglobin increase  $\geq 1.5$  g/dL
- Duration of Response (RBC Transfusion Independency, HI-N, HI-P, HI-E or Objective Response)
- Overall Objective Response (OR) [Complete Response (CR), Partial Response (PR), and Hematologic Improvement (HI)]

Proprietary confidential information.

© 2019 Boehringer Ingelheim International GmbH or one or more of its affiliated companies. All rights reserved.

This document may not - in full or in part - be passed on, reproduced, published or otherwise used without prior written permission.

## 5.1.2 Assessment of efficacy

### 5.1.2.1 Bone marrow aspirate and peripheral blood

Response will be assessed in bone marrow (BM), peripheral blood and clinically as specified in the [Flow Chart](#).

The investigator's overall assessment of the disease and confirmation of non-PD/non-relapse status will be required for the decision to continue with the next cycle of study treatment.

At baseline a BM aspirate is required. A BM biopsy will be required if aspiration is inadequate. During response assessment after treatment initiation, a BM aspirate will be sufficient and no BM biopsy will be required unless the aspirate results in a *punctio sicca* (dry tap) in which case a BM biopsy will be performed. The first scheduled bone marrow sample for response assessment will be performed at the end of Cycle 4. The BM aspirate (or biopsy if aspirate is inadequate) will be scheduled for response assessment at the EOC4 and at the time of disease progression/relapse or EOT, whichever occurs first. The classification of response is defined in Section 5.1.2.3.

An unscheduled BM examination should be performed as soon as possible when progression or relapse of MDS is suspected (based on clinical or laboratory findings) irrespective of the next scheduled BM assessment.

### 5.1.2.3 Assessment and definition of response criteria

Response to treatment will be evaluated according to the International Working Group (IWG) 2006 criteria ([R13-0369](#)). The evaluation period for transfusion independence and response will last from randomization (for phase II / first administration for phase I) until discontinuation of treatment.

### Transfusion independence (TI)

- Red blood cell (RBC) transfusion independence and platelet transfusion independence will be evaluated in patients who are transfusion dependent at baseline. Percentages will be calculated using all treated patients as the denominator.
- A patient is considered transfusion independent at baseline if the patient has had no transfusions during the 56 days prior to and including the first day of treatment. Otherwise, the patient is considered to be transfusion dependent.
- A patient is considered transfusion independent if the patient has had no transfusions over the course of  $\geq 56$  consecutive days.

### Hematologic improvement (HI)

The HI will be evaluated in patients with abnormal pretreatment values defined as follows:

- Erythroid response (HI-E): Patients with a pretreatment hemoglobin  $<11$  g/dL demonstrate erythroid response if their hemoglobin increases by  $\geq 1.5$  g/dL for at least eight weeks, and there is a reduction in the units of red cell transfusions by an absolute number of at least four red cell transfusions per eight weeks compared with the pretreatment transfusion number in the previous eight weeks. Only red cell transfusions given for a hemoglobin  $\leq 9$  g/dL pretreatment will count in the red cell transfusion response evaluation.
- Platelet response (HI-P) — Patients with a pretreatment platelet count  $<100 \times 10^9/L$  demonstrate a platelet response if there is an absolute platelet increase of  $\geq 30 \times 10^9/L$  for patients starting with  $>20 \times 10^9/L$  platelets. For those with an increase from  $10 \times 10^9/L$  to  $>20 \times 10^9/L$  must have an increase of at least 100 percent.
- Neutrophil response (HI-N) — Patients with a pretreatment neutrophil count  $<1 \times 10^9/L$  demonstrate a neutrophil response if they have an at least 100 percent increase and an absolute increase  $>0.5 \times 10^9/L$ .
- Mean hemoglobin increase  $\geq 1.5$  g/dL — Time Frame: Up to approximately 48 weeks. Proportion of subjects achieving hemoglobin (Hgb) increase from baseline  $\geq 1.5$  g/dL over any consecutive 56-day period in absence of Red blood cell (RBC) transfusions.

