#### 3.3.2 Inclusion criteria

1. Documented diagnosis of MDS according to World Health Organization (WHO) criteria that meets International Prognostic Scoring System (IPSS) classification of low or intermediate-1 risk disease at screening as determined by microscopic and standard cytogenetic analyses of the bone marrow and peripheral complete blood count (CBC).
  - Phase I dose escalation: patients who experienced ESA treatment failure or do not qualify (serum erythropoietin level > 500 U) for ESA treatment, and are refractory to or not amenable or eligible for established MDS therapy (HMA, lenalidomide)

Proprietary confidential information.

- Phase I expansion:
    - *Expansion cohort 1* (“pre-treated”): patients who experienced ESA treatment failure or do not qualify (serum erythropoietin level > 500 U) for ESA treatment and are refractory to established MDS therapy (HMA and /or lenalidomide)
    - *Expansion cohort 2* (“untreated”): patients who experienced ESA treatment failure or do not qualify (serum erythropoietin level > 500 U) for ESA treatment and who have not received prior HMA and/or lenalidomide (because not amenable or eligible for these treatments)
  - Phase II: patients who experienced ESA treatment failure or do not qualify (serum erythropoietin level > 500 U) for ESA treatment. For definition of further details of the phase II patients to be included the protocol will be amended based on Phase I results.
2. Patient has the evidence of symptomatic anemia according to the following criteria:
    - Phase I only: patients must have mean hemoglobin concentration < 10.0 g/dL of 2 measurements (not influenced by RBC transfusion within 7 days of measurement) and having received < 4 units of RBCs within 8 weeks prior to start of treatment OR,
    - Phase I/II: Patients must have received  $\geq 2$  units of RBCs for hemoglobin  $\leq 9.0$  g/dL within 8 weeks prior to start of treatment.
  3. Patient is non-responsive to, refractory to, or intolerant of ESAs, or ESAs are contraindicated or unavailable, or a documented serum erythropoietin level of > 500 U/L.
  4. Eastern Cooperative Oncology Group (ECOG) Performance Status  $\leq 2$  (refer to [Section 10.2](#)) (R14-0080).
  5. Age  $\geq 18$  years.
  6. Written informed consent which is consistent with International Conference on Harmonization – Good Clinical Practice (ICH-GCP) guidelines and local legislation.

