#### 6.2.1 Screening and run-in period(s)

The screening period (Visit 1), i.e. the phase after informed consent and before the first administration of the trial drug, may be as long as 21 days. The site should call Interactive Response Technologies (IRT) after informed consent is signed to register the patient as enrolled.

The patient will be officially entered (randomized for Phase II) via IRT after all the eligibility criteria are met.

The following parameters and investigations will be obtained and / or performed:

- Informed consent
- Demographics (sex, birth date, race) and baseline conditions

Proprietary confidential information.

© 2019 Boehringer Ingelheim International GmbH or one or more of its affiliated companies. All rights reserved.

This document may not - in full or in part - be passed on, reproduced, published or otherwise used without prior written permission.

- Medical history
  - Review of inclusion and exclusion criteria (patient eligibility)
  - Dose assignment (during cohort dose escalation of Phase I only, before the first administration of the trial drug and after informed consent and review of in- and exclusion criteria)
  - Safety laboratory (hematology, biochemistry including serum immunoglobulin levels and direct antiglobulin test, coagulation, urine; for details please refer to [Section 5.2.3.1](#))
  - Physical examination, height, weight, vital signs and ECOG performance score
  - Serum pregnancy test in women of childbearing potential
  - 12-lead ECG
  - Adverse Events
  - Concomitant therapy
  - Bone marrow aspiration for disease assessment
  - Molecular genetics and cytogenetics of MDS (Historical/available data for Phase I patients and required at screening for Phase II patients)
  - Number of transfusions (up to 3 months prior to start of treatment)
- Phase II: Randomization may be at the latest performed on Cycle 1 Visit 1, but before start of therapy

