5.2.2 Secondary endpoints

The secondary endpoints in Phase I are

- RBC Transfusion Independence (RBC TI)
- Hematologic improvement neutrophils (HI-N)
- Hematologic improvement platelets (HI-P)
- Hematologic improvement erythroid (HI-E)
- Time to HI-E response
- Mean hemoglobin increase ≥ 1.5 g/dL
- Duration of Response (RBC Transfusion Independence, HI-N, HI-P, HI-E or Objective Response)
- Overall Objective Response (OR) [Complete Response (CR), Partial Response (PR), and Hematologic Improvement (HI)]

RBC Transfusion Independence (RBC-TI):

The definition of RBC TI is given in section 5.1.2.3 of the CTP. RBC-TI is evaluated in patients who are transfusion dependent at baseline. Percentages will be calculated using all treated patients, who are transfusion dependent at baseline, as the denominator.

The investigator's assessment as reported on the "Disease Assessment eCRF" will be used for the analysis of this endpoint. No derivation from the "Concomitant Blood Product Therapies eCRF" is planned. Consistency between these two eCRF pages will be reviewed during the trial's Medical Quality Review Meetings (MQRMs).

HI-N, HI-P and HI-E:

HI-N, HI-P and HI-E are defined in section 5.1.2.3 of the CTP. The investigator's assessment as reported on the "Disease Assessment eCRF" will be used for the analysis of these endpoints. No derivation from the "Laboratory eCRF" (or the "Concomitant Blood Product Therapies eCRF") is planned. Consistency between these eCRF pages will be reviewed during the trial's Medical Quality Review Meetings (MQRMs).

Time to HI-E response:

Time to HI-E response is defined only for patients who achieve a HI-E response as follows:

Time to HI-E response [days] = date of first assessment indicating HI-E response – date of first administration of trial medication + 1.

Mean hemoglobin increase ≥ 1.5 g/dL:

The definition of "Mean hemoglobin increase ≥ 1.5 g/dL" is given in CTP section 5.1.2.3.

Duration of Response:

Duration of objective response is defined only for patients who achieve an overall response of CR or mCR or RBC TI.

Duration of response is defined as:

Duration of Response [days] = date of outcome – date of first assessment indicating CR or mCR or RBC TI after first administration of trial medication + 1.

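### HI-E as written cannot be met by Phase I patients who enter with fewer than 4 countable red cell units, yet the SAP by default keeps them in its denominator

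*Protocol*

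**What the plan says.** **Definition.** Protocol 5.1.2.3 (Hematologic improvement) joins two HI-E conditions. Haemoglobin must be up by 1.5 g/dL or more for eight weeks or longer, "and there is a reduction in the units of red cell transfusions by an absolute number of at least four red cell transfusions", counted over an eight-week period and measured against the eight weeks before treatment. Only units given at a haemoglobin of 9 g/dL or lower "pretreatment will count in the red cell transfusion response evaluation". Earlier in the same section the protocol also says: "Response to treatment will be evaluated according to the International Working Group (IWG) 2006 criteria".

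**Entry.** Protocol 3.3.2, criterion 2, gives Phase I patients two routes. The first asks for a mean haemoglobin under 10.0 g/dL and "having received < 4 units of RBCs within 8 weeks prior to start of treatment". The second asks for at least 2 units, given for haemoglobin of 9.0 g/dL or lower, in the same eight weeks.

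**Analysis.** SAP 5.2.2 says "HI-N, HI-P and HI-E are defined in section 5.1.2.3 of the CTP". It takes the result from the investigator's Disease Assessment eCRF entry, plans no derivation from laboratory or transfusion records, and leaves consistency to the Medical Quality Review Meetings (MQRMs). For RBC transfusion independence (RBC-TI) the same section narrows the base: "Percentages will be calculated using all treated patients, who are transfusion dependent at baseline, as the denominator". HI-E has no such rule. SAP 6.3 assigns efficacy to the treated set. SAP 7 bases percentages on everyone in the set unless another rule is given. SAP 7.5.2 tabulates HI-E and overall objective response by dose cohort and in total, without inference.

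**The concern.** The entry criterion admits patients for whom the endpoint cannot be reached. A patient with 2 units before treatment who becomes fully transfusion independent, with a lasting haemoglobin gain, still fails the written HI-E rule, because 2 units cannot fall by 4. The SAP corrected the parallel problem for RBC-TI: the protocol's denominator there was all treated patients, and the SAP limited it to those transfusion dependent at baseline. It made no such correction for HI-E.

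This affects what the HI-E row of the efficacy table means. A low percentage could reflect little erythroid activity, or many patients who could not qualify, and the planned table does not separate the two. HI-E is also a component of overall objective response (SAP 5.2.2), so a patient whose only response would be erythroid is lost there too.

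**Working it through.** The plan states no target or expected rate for HI-E, so there is no figure of its own to reproduce. The check is one of feasibility.

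1. **Inputs.** Required fall: 4 units per eight weeks (Protocol 5.1.2.3). Phase I patients: 21 in dose escalation + 6 in expansion = 27 (Protocol synopsis), taken here as the treated set. Let b be a patient's countable units in the eight weeks before treatment.

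2. **Largest possible fall.** On-treatment units cannot go below 0, so the largest fall is b − 0 = b.
   - b = 0, 1, 2 or 3: largest fall 0, 1, 2 or 3, always short of 4. HI-E is unattainable.
   - b = 4 or more: largest fall at least 4. HI-E is attainable.

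3. **Who is affected.** Every patient who meets the first entry route has 0 to 3 total units, hence at most 3 countable. Second-route patients with 2 or 3 countable units are also blocked. That includes anyone with 4 or more total units of which fewer than 4 were given at haemoglobin 9 g/dL or lower.

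4. **Do they leave the denominator?** Protocol 5.1.2.3 limits HI-E evaluation to pretreatment haemoglobin below 11 g/dL. Even if that is read as a denominator rule, it sets no minimum transfusion burden, and a first-route patient with mean haemoglobin below 10.0 g/dL passes it. By the SAP default, the blocked patients stay in.

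5. **Ceiling, if the text was applied.** With k blocked patients, the highest possible HI-E percentage is (27 − k)/27. The documents do not give k; these values are assumptions:
   - k = 7: 20/27 = 74.1%
   - k = 14: 13/27 = 48.1%
   - k = 20: 7/27 = 25.9%
   - full range: k = 0 gives 100%, k = 27 gives 0%

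   The same factor links the two ways of reporting: treated-set percentage = percentage among patients able to respond × (27 − k)/27.

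6. **Within a cohort.** Protocol 4.1.3 allows cohorts of three to six. In a cohort of 3 with j blocked, the ceiling is (3 − j)/3: 100%, 67%, 33% or 0% for j = 0, 1, 2 or 3. Two dose levels can therefore differ in HI-E because of baseline transfusion burden alone.

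**The case against.** The strongest reply is that HI-E is not computed from the written rule. The investigator records it, the protocol cites IWG 2006, and the MQRMs review consistency. An investigator may have credited a haemoglobin rise alone, in which case no patient was blocked. This stands as a limit on the consequence: the ceilings hold only if the text was applied. It does not remove the defect, because the reported HI-E would then differ from the definition the SAP cites. The cited criteria are not part of the documents, so they cannot settle which reading was used.

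The second reply is that erythroid benefit is measured elsewhere. This also stands. Patients with 1 to 3 units in the 56 days before treatment count as transfusion dependent and are evaluable for RBC-TI. The 56-day haemoglobin endpoint has no 4-unit condition and covers patients with 0 units as well. Both are tabulated by dose cohort. Neither, however, is a component of overall objective response.

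The third concerns the remedy. One might want to redefine HI-E as haemoglobin alone for patients with fewer than 4 units. That would give the lower-burden group the easier criterion and reverse the SAP's choice not to derive HI-E. If a transfusion disqualified the window, it would largely relabel the existing 56-day haemoglobin endpoint. If it did not, a rise produced by transfusion could count. That objection is sound, and the fix below avoids redefinition.

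**Conclusion.** The definition and the entry criterion conflict on their face: the written HI-E rule is arithmetically impossible for any patient with 3 or fewer countable units, and the SAP neither adapts the rule nor restricts the denominator. Either these patients are structural non-responders for HI-E and for its part in overall objective response, or reported HI-E does not match its stated definition.

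A reader might infer that the HI-E and overall response rates are certainly understated, or that the trial cannot detect erythroid benefit in low-burden patients. The documents support neither. They do not show how investigators applied the rule or how many of the 27 are affected, and two other endpoints register such benefit. The only firm figures are the 4-unit threshold and N = 27; every value of k is assumed.

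Severity is minor: the endpoints are secondary and descriptive, SAP 7.5.2 plans no inference, and Phase II was not run (SAP 4.2).

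**What to change.** In SAP 5.2.2, declared under SAP 4.2, reconcile the HI-E definition with inclusion criterion 2 for reporting:

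- Keep the investigator-reported HI-E. Tabulate it within dose cohort and in total by RBC units in the eight weeks before treatment: fewer than 4, or 4 or more. Use countable units where the pre-transfusion haemoglobin was recorded, and total units otherwise.
- Beside the treated-set percentage, give the percentage among patients able to meet the written definition.
- Footnote HI-E and overall objective response with the number of patients who cannot meet that definition.
- At the planned MQRMs, identify any HI-E response recorded in a patient with fewer than 4 units, since it departs from the written rule. This would also show which reading investigators used.
- For the group with fewer than 4 units, show the 56-day haemoglobin endpoint beside HI-E under its own name.

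The grouping uses data already collected: Protocol 6.2.1 lists "Number of transfusions (up to 3 months prior to start of treatment" at screening, and SAP 5.2.2 refers to a blood product eCRF. The reduced data collection under CTP version 5.0 concerns cycle 5 onward and does not touch this baseline count.

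The cost is SAP wording, one baseline grouping, an extra table split and a footnote. The downsides are a late, declared reporting change and small subgroup counts. Where pre-transfusion haemoglobin is missing, patients with 4 or more total but fewer than 4 countable units would be misplaced among those able to respond.

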#### 4.1.4 Drug assignment and administration of doses for each patient

Prior to inclusion of a new patient during the cohort dose escalation phase, the Investigator has to confirm the actual dose tier of BI 836858 for the patient with the Sponsor who oversees the cohort dose escalation steps and the safety data of patients from all trial sites. BI 836858 will be administered as an intravenous infusion every 14 days under the supervision of the Investigator or designated personnel.

BI 836858 may be administered at any time during the day.

it is recommended to

start the infusion during the morning hours.

Premedication to prevent infusion-related reactions is obligatory 30 minutes (up to 120 min before start of administration of BI 836858 is permissible) prior to the first and second administration of BI 836858, unless a contraindication for premedication exists, and should include:

- Acetaminophen/Paracetamol 650 mg - 1000 mg p.o., or equivalent
- Antihistamine p.o. or i.v., equivalent to Diphenhydramine 50 mg i.v.
- Glucocorticoid i.v., equivalent to prednisolone 100 mg

If BI 836858 has been well tolerated without signs of infusion-related reactions in the first administration, glucocorticoid premedication may be reduced to a dose equivalent to 50 mg prednisolone for the second through fourth administrations, and in case this is well tolerated reduce the glucocorticoid with the 5th infusion (25 mg with the 5th and 0 mg with the 6th infusion.) However, in case an administration of BI 836858 was not well tolerated the premedication with prednisolone can be re-escalated up to 100 mg.

Before the administration of BI 836858, adverse events and safety laboratory will be assessed. To start or continue treatment with further administrations, all of the following criteria must be met:

- (1) Neutrophils  $\geq 1000 /\mu\text{L}$  ( $1.0 \times 10^9/\text{L}$ )
- (2) Platelets  $\geq 50,000 /\mu\text{L}$  ( $50 \times 10^9/\text{L}$ ), unless CTCAE Grade 3 or 4 thrombocytopenia was preexistent prior to trial entry. Patients who go from Grade 3 to Grade 4 thrombocytopenia after treatment may continue on study provided that post-transfusion platelet count is at least 20,000/uL before therapy is given.
- (3) Acceptable tolerability (in case of an AE at the planned start of a further administration, patients may continue therapy only after recovery to a level which would allow further therapy, i.e. CTCAE grade 1 or baseline value.)

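### The HI-P rule in protocol 5.1.2.3 sets no platelet criterion for starts of 20 x10^9/L or below except exactly 10, where its percentage condition is always met

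*Protocol*

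**What the plan says.** Protocol 5.1.2.3 begins with the governing sentence: "Response to treatment will be evaluated according to the International Working Group (IWG) 2006 criteria". The platelet criterion itself appears only in the HI-P bullet of that section. The bullet applies to "Patients with a pretreatment platelet count" below 100 x10^9/L, with no lower bound, and has two parts:

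- Patients starting above 20 x10^9/L need an absolute rise of at least 30 x10^9/L.
- The second part opens "For those with an increase from" 10 x10^9/L to above 20 x10^9/L, and says these patients "must have an increase of at least 100 percent". The 10 is printed as a single value, with no inequality sign and no range.

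Patients with counts this low can be in the trial. Protocol 3.3.3 has no platelet exclusion. Section 4.1.4 asks for 50,000/µL (50 x10^9/L) before dosing "unless CTCAE Grade 3 or 4 thrombocytopenia was preexistent prior to trial entry". Section 2.2 allows del(5q) patients in Phase I who do not qualify for lenalidomide because platelets are below 50,000/µL.

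The SAP adds no definition. Its section 5.2.2 says "HI-N, HI-P and HI-E are defined in section 5.1.2.3 of the CTP". It adds that the investigator's entry on the Disease Assessment eCRF "will be used for the analysis of these endpoints", with nothing derived from the Laboratory eCRF. Agreement between the eCRF pages is to be reviewed at the Medical Quality Review Meetings (MQRMs). In the same section, a single reported HI-P is enough to make Overall Objective Response positive. SAP 7.5.2 tabulates both endpoints by dose cohort and in total, without inference.

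**The concern.** A condition that cannot fail suggests that the sentence does not say what was meant. If the second part is limited to a start of 10, its percentage requirement does nothing, and patients starting elsewhere at or below 20 fall under neither part although the bullet includes them in the evaluation. Two sites could then record the same platelet course differently. One could follow the printed sentence and enter no response; another could follow the cited IWG 2006 criteria, or its own reading of the sentence, and enter a response. The analysis takes the investigator's entry as it stands, so the difference would pass into the HI-P table and, for a patient with no other qualifying response, into Overall Objective Response. The eCRF consistency review is the natural place to catch this, but for these baselines the documents give it no threshold to check against.

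**Working it through.** There is no plan figure to reproduce; the check is of the rule itself. Write b for the baseline and p for the later count, both in x10^9/L. Percentage rise = 100 × (p − b)/b.

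**1. At the one start covered.** With b = 10 and p > 20, the rise exceeds 100 × (20 − 10)/10 = 100%. For example, p = 20.1 gives 101% and p = 21 gives 110%. The requirement of at least 100% is always met.

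**2. At other starts of 20 or below.** The first part needs b > 20 and the second is printed for b = 10. Of the 20 whole-number starts from 1 to 20, 19 have no criterion. On a 0.1 grid from 1.0 to 20.0, 190 of 191 values have none.

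**3. When the percentage could matter.** For a rise to above 20, the 100% condition adds something only if doubling b takes the count beyond 20, that is, if b > 10. For b = 15, doubling means p ≥ 30; for b = 20, p ≥ 40.

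**4. Looser readings of the second part.**

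| Reading of the starting value | Whole-number starts still without a rule | Where the 100% condition has effect |
|---|---|---|
| Exactly 10, as printed | 1–9 and 11–20 | nowhere |
| A: 10 to 20 | 1–9 | 11–20 |
| B: 10 or below | 11–20 | nowhere |
| C: 20 or below | none | 11–20 |

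Only reading C both closes the gap and gives the percentage a function. The printed 10 does not say it.

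**5. Example courses.**

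- 15 to 35: rise 20, or 20/15 = 133%. It meets neither printed part, so it is a non-response if the text is applied. It is a response under A or C.
- 15 to 21: rise 6, or 6/15 = 40%. It is not a response as printed or under A, B or C.

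**6. Size.** The protocol synopsis gives 21 + 6 = 27 Phase I patients. One changed patient is 1/27 = 3.7 percentage points overall. In a dose cohort of 3, the usual minimum in protocol 4.1.3, it is 1/3 = 33 points. The number of patients with a baseline of 20 or below is not given.

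**The case against.** The strongest reply is that 5.1.2.3 names IWG 2006 as the governing criteria, so an investigator has a source with which to settle a badly worded sentence. That stands, and it limits the point. A reader might infer that these patients cannot be classified at all. The documents do not support that: the investigator still records a response or none, and the printed text taken strictly returns non-response. What remains is that the printed sentence and the cited source may lead to different entries, and neither document says which prevails.

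A second reply is that SAP 5.2.2 already plans to compare the eCRF pages. That also stands, but the comparison needs a rule.

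A third is that a symbol was lost when the text was read from the PDF. The other signs in the bullet (<100, ≥30, >20) are intact. A lost sign making it 10 or below would give reading B, which leaves 11–20 without a rule and the percentage idle.

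A reader might also infer that every patient with a baseline of 20 or below is affected. That goes too far. A start of exactly 10 has a rule, and a patient whose count does not rise appreciably is a non-responder on all four readings in the table. Only a rise on which the readings differ matters. Overall Objective Response changes only if that patient has no CR, PR, HI-N or HI-E.

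Finally, the replacement threshold cannot be settled from these documents, because the IWG 2006 platelet text is not reproduced in them. That is correct, and the fix allows for it.

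**Conclusion.** The second HI-P sentence is wrong as written. It covers one starting value, at which its condition is empty, and it leaves the other baselines of 20 x10^9/L or below without a criterion. The SAP carries this forward unchanged. It is a drafting defect in one descriptive Phase I secondary endpoint, with a possible effect on Overall Objective Response. The figures of 3.7 points overall and 33 points in a cohort of 3 are ceilings per changed patient, and the true effect may be zero. The conclusion rests on taking the printed 10 as a single value; readings A and B narrow the gap but do not close it. A reader might infer that the dose conclusions are in doubt. They are not, because MTD and DLT do not use HI-P. Phase II was not run.

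**What to change.** 1. In SAP 5.2.2, reconcile the sentence with the platelet criterion in the cited IWG 2006 publication and state one rule for all starts of 20 x10^9/L or below. The reading that closes the gap and makes the percentage matter is a rise to above 20 x10^9/L and by at least 100%. Confirm it against the source before adopting it.
2. List the patients with baseline platelets of 20 x10^9/L or below.
3. At the planned MQRM review, check their HI-P entries against that rule. Restating the rule alone would not change the tables, because the analysis uses the investigator's entry.
4. If no patient qualifies, a footnote to the HI-P table closes the matter.

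The cost is one sentence, one short listing and a check of whatever patients it shows. Baseline counts are already collected at screening and on Day 1. One limit applies: after protocol version 5.0, laboratory tests from Cycle 5 onward are no longer mandatory and are entered in the eCRF only when they qualify as an adverse event. A late HI-P entry may therefore have no count to check against, and the listing should say so.
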